## **PACU Hospitalization:**

• 0th postoperative day (4 hours after general anesthesia), 1st postoperative day, 2nd postoperative day = exit screening

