#### ORTOPOD PILOT STUDY

#### **MARCH 1 2025**

**ORTOPOD PILOT STUDY** is a non-randomized, non-interventional clinical study that addresses the issue of perioperative neurocognitive disorder (deterioration of cognitive functions in the preoperative and perioperative period) and its impact on the occurrence of postoperative delirium.

Respondents meeting the entry criteria will undergo elective orthopaedic surgery (total hip arthroplasty) under general or regional anaesthesia. Preoperatively, they will be examined using the ALBA and POBAV tests, which serve for rapid and indicative assessment of cognitive functions. Furthermore, the functional capacity of patients will be assessed using the Clinical Frailty Scale, and depression will be evaluated using the Geriatric Depression Scale (questionnaire).

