# After the procedure, during hospitalization in the ICU/PACU, screening for postoperative delirium will be conducted using the CAM-ICU tool.

The aim of the pilot study is to verify the methodology and obtain baseline data on the incidence of cognitive dysfunction, depression, and frailty preoperatively, as well as the incidence of postoperative delirium in this group of patients before submitting a grant to AZV ČR. The main research question will be whether preoperative cognitive decline (according to the ALBA and POBAV tests) is associated with the occurrence of postoperative delirium. The second research question will be what percentage of patients with preoperative cognitive deficit (according to the ALBA and POBAV tests) undergo elective total hip arthroplasty. Secondary outcomes will include whether there are differences in the ALBA and POBAV test results before and after surgery (cognitive decline after anesthesia and surgery), whether higher Clinical Frailty Scale scores are associated with the occurrence of postoperative delirium, and whether the results on the Geriatric Depression Scale change preoperatively and postoperatively.

Key words: postoperative delirium, screening, senior, risk factors, cognitive assessment, CAM-ICU, Amnesia Light and Brief Assessment (ALBA), POBAV

The study involves a homogeneous group of patients undergoing total hip arthroplasty under general or regional anesthesia. Patients meeting the study's entry criteria, who have signed informed consent to participate in the study, will be included.

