## **ICU Hospitalization:**

• 0th postoperative day (4 hours after general anesthesia), 1st postoperative day, 2nd postoperative day, screening during ICU hospitalization, final screening upon discharge from ICU = exit screening

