## **ENTRY CRITERIA:**

- Age over 65 years (inclusive)
- Type of procedure: elective total hip arthroplasty under general or regional anesthesia
- ASA classification I-III
- Absence of sensory impairment (blindness, deafness, deaf-muteness)
- Postoperative hospitalization in the intensive care unit, post-anesthesia care unit (PACU)

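### Does timing the day-0 CAM-ICU screen only from general anaesthesia leave regional-anaesthesia patients without a usable first delirium assessment?

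*Protocol*

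**What the plan says.** Eligibility covers both types of anaesthesia in three places. The opening description speaks of "elective orthopaedic surgery (total hip arthroplasty) under general or regional anaesthesia". The account of the study population says "The study involves a homogeneous group of patients undergoing total hip arthroplasty under general or regional anesthesia". Under Entry Criteria the item is "Type of procedure: elective total hip arthroplasty under general or regional anesthesia".

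Delirium screening is announced for all of these patients: "during hospitalization in the ICU/PACU, screening for postoperative delirium will be conducted using the CAM-ICU tool". The detail follows in two schedules. Under PACU Hospitalization it is "0th postoperative day (4 hours after general anesthesia), 1st postoperative day, 2nd postoperative day = exit screening". Under ICU Hospitalization it is "0th postoperative day (4 hours after general anesthesia), 1st postoperative day, 2nd postoperative day, screening during ICU hospitalization", followed by a final screen at ICU discharge. The Postoperatively section adds that ICU patients are screened at least daily. Once delirium has developed, screening is every 12 hours. None of these other lines gives a day-0 hour.

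**The concern.** Both schedules describe day 0 as "0th postoperative day (4 hours after general anesthesia", and a patient operated on under regional anaesthesia has no general anaesthetic to count from. Read literally, the only routine screen with a stated number of hours is timed for one of the two groups admitted and left open for the other. A very literal reader might even conclude that regional patients have no timed day-0 screen.

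This would matter because CAM-ICU is the only delirium instrument named, delirium is the outcome of the main research question, and its incidence is one of the baseline figures wanted before the grant application. Type of anaesthesia is not randomised. If the first screen came systematically earlier or later in one group, brief early delirium might be detected more often in that group. The pilot also sets out to test its own procedures ("The aim of the pilot study is to verify the methodology and obtain baseline data"), so one would like the schedule to fit every patient it admits.

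**Working it through.** The Protocol states no sample size, event rate or split by type of anaesthesia, so there is no figure to reproduce. The check compares the sections and counts screens.

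**1. Is there a stated day-0 hour for regional patients anywhere?**

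| Protocol section | Applies to regional patients? | Day-0 hour given for them? |
|---|---|---|
| General statement on CAM-ICU screening in ICU/PACU | yes | no |
| Postoperatively (at least daily, ICU) | yes, in the ICU | no |
| ICU Hospitalization | day 0 is listed without restriction; the 4 hours refer to general anaesthesia | no |
| PACU Hospitalization | same | no |
| In case of postoperative delirium development (12-hourly) | only once delirium is present | no |

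The hour is therefore missing in both schedules, and no other section supplies it.

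**2. Are any screens lost?** In the PACU list the screens are days 0, 1 and 2, which makes 3. The calendar days are not limited by type of anaesthesia, so the count is 3 of 3 for general and 3 of 3 for regional. Of these, 1 of 3 carries a clock time after general anaesthesia and 0 of 3 after regional. In the ICU, daily screening and the discharge screen come on top for both groups. The difference lies in the timing of one screen, not in the number of assessments.

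**3. What must happen for the missing hour to change a result?** Assume that a patient counts as having delirium if any screen is positive. The Protocol does not spell this out, but it is the natural reading of occurrence. The day-0 hour then changes a patient's classification only if all of the following hold:

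- the patient had regional anaesthesia;
- delirium would be seen at one hour of day 0 and not at another;
- every later screen (days 1 and 2, plus the additional ICU screens where they apply) is negative.

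Delirium that is still present on day 1 or day 2 can be picked up by screens common to both groups.

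**4. What must happen for the main association to be biased?** Beyond step 3, the misclassification would have to be related to preoperative ALBA or POBAV results, for example because type of anaesthesia is chosen partly by cognitive state. That is possible, but the document gives nothing from which to judge its size.

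**5. How wide could the timing gap be?** If surgery ends at clock hour h and day 0 ends at midnight, a regional patient's screen can fall anywhere from 0 to 24 − h hours after surgery. With h = 10 this is 0 to 24 − 10 = 14 hours; with h = 16 it is 0 to 24 − 16 = 8 hours. Both values of h are assumptions. The calculation also treats every hour up to midnight as a plausible screening time, so it is an outer limit on timing and says nothing about incidence.

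**The case for a change.** The best argument for a change is that the Protocol chose to fix this time and did so for only part of its population. When a bedside assessment takes place is a data-collection instruction, not something an analysis plan can supply later. The document itself separates general from regional anaesthesia, so a reader cannot be sure that the 4 hours were meant for everyone. The correction would be one phrase in two lines, and a pilot is the place to find such things.

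The textual part of this stands: the wording is incomplete, and nothing suggests that removed text or a conversion fault explains it. The consequences drawn from it do not stand.

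- It is true that a screen at a common hour cannot be recreated afterwards. But occurrence over the stay does not need a common hour, and the Protocol sets none for days 1 and 2 in any patient.
- The general-anaesthesia time is looser than it appears. No tolerance is given, nor is it said whether the 4 hours start at the end of anaesthesia, at extubation or at another event. The contrast between a sharp time point in one group and an open window in the other is therefore overstated.
- The bracketed phrase may be a condition specific to general anaesthesia, with the calendar day sufficing for regional patients. The Protocol gives no reason for the phrase, so this remains only a possible reading. Even so, requiring one identical interval for both groups would be a preference and not the repair of an error.

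**Conclusion.** The concern is right about the wording and does not call for a change to the plan. The gap amounts to one unstated hour on one screen. No assessment is lost, the later screens are shared, and the outcome is whether delirium occurred at all during the screened stay. Staff carrying out a day-0 screen after regional anaesthesia will have to choose an hour, and any sensible choice serves the question the pilot asks.

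This rests on two assumptions: that occurrence means a positive result on any screen, and that regional patients are in fact screened on day 0, as the lists and the general screening statement imply. The effect on delirium incidence, or on its association with preoperative cognition, cannot be calculated from the document. Given the conditions that must coincide, it is probably small, and nothing in the Protocol shows that it would be material.

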## In case of postoperative delirium development:

• Screening 2 times a day, every 12 hours

## **ENTRY CRITERIA:**

- Age over 65 years (inclusive)
- Type of procedure: elective total hip arthroplasty under general or regional anesthesia
- ASA classification I-III
- Absence of sensory impairment (blindness, deafness, deaf-muteness)
- Postoperative hospitalization in the intensive care unit, post-anesthesia care unit (PACU)

#### **EXCLUSION CRITERIA:**

- Glasgow Coma Scale 14 or less
- Limited legal capacity
- Known psychiatric illness with the use of psychiatric medications

- Effect of premedication, psychiatric, and analgesic-sedative drugs (at the time of cognitive function testing)
  Active oncological disease
  Chronic use of strong opioids
  Re-operation
